1.17 PREPARATION/HANDLING/STORAGE/ACCOUNTABILITY

1.17.1 ACQUISITION AND ACCOUNTABILITY

Randomization, drug and placebo preparation, and packaging will be done by our Jackson research pharmacy following their established protocols for double-blind studies. When ordered, the loading dose will be administered by nursing staff prior to discharge. The remaining outpatient supply will be delivered by the pharmacy to the Ryder Trauma nursing staff to be provided to the patient, along with instructions, upon discharge. If doses are missed, patients will be instructed to return unused product at their follow up visit.

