1.16.2 DOSING AND ADMINISTRATION

NAC or placebo will be administered orally as a 4 gram loading dose, followed by 2 g PO BID for 4 days, then 1.5 g PO BID for 2 days. The loading dose will be given prior to discharge from Ryder Trauma center. Remaining doses will begin on the following morning as an outpatient to complete the 1 week treatment course. Delayed doses may be taken late if noted before the next dose, and otherwise will be skipped. The doses may be taken with or without meals.

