1.19 STUDY INTERVENTION COMPLIANCE

The loading dose will be given prior to discharge. The remaining study drug will be taken as an outpatient over the next 6 days. We will ask participants to complete a study drug log to record timing of each dose. We will not plan any labs or assays for verification. Drug log will be collected at the first outpatient visit.

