1.22 PARTICIPANT DISCONTINUATION/WITHDRAWAL FROM THE STUDY

Participants are free to withdraw from participation in the study at any time upon request.

An investigator may discontinue or withdraw a participant from the study for the following reasons:

- Pregnancy
- Significant study intervention non-compliance
- If any clinical adverse event (AE), laboratory abnormality, or other medical condition or situation occurs such that continued participation in the study would not be in the best interest of the participant
- If the participant meets an exclusion criterion (either newly developed or not previously recognized) that precludes further study participation

The reason for participant discontinuation or withdrawal from the study will be recorded on the NAC Case Report Form (CRF). Subjects who sign the informed consent form and are randomized but do not receive the study intervention may be replaced. Subjects who sign the informed consent form, and are randomized and receive the study intervention, and subsequently withdraw, or are withdrawn or discontinued from the study, will be replaced. Patients who do not complete the full course of study drug/placebo will be noted in the results tables, and they will not be included in the statistical analysis of outcome measures, since this is a simple comparison of SIT score between patients receiving a 1 week course of NAC versus placebo.

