1.25 SAFETY AND OTHER ASSESSMENTS

Screening for, or participation in, this study will not alter head trauma standard of care. The potential patient safety issue for the study is the possibility of adverse reaction to study medication. The dosage regimen we are using has been used in a previous published trial with no adverse events reported. Nonetheless, we are giving the initial loading dose prior to discharge, which will enable us to identify any immediate events such as acute allergic reaction. Patients will receive instructions and contact information to inform the coordinator or PI promptly of any potential problems. At follow up visit, we will collect patient drug logs and any comments or notes regarding possible side effects.

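### Twelve of 13 doses are taken at home with no scheduled contact until Visit 2, and nothing independent can check a drug log that reports full adherence.

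*Combined protocol and SAP*

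**What the plan says.** Section 1.16.2 gives the regimen after the 4 g loading dose: "followed by 2 g PO BID for 4 days, then 1.5 g PO BID for 2 days". It also fixes where the first dose is taken: "The loading dose will be given prior to discharge from Ryder Trauma center". Section 1.19 covers the rest: "The remaining study drug will be taken as an outpatient over the next 6 days".

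Four places deal with adherence:

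- **Section 1.19** sets up the record, "We will ask participants to complete a study drug log to record timing of each dose", and then limits how it is checked: "We will not plan any labs or assays for verification. Drug log will be collected at the first outpatient visit".
- **Section 1.17.1** deals with product: "If doses are missed, patients will be instructed to return unused product at their follow up visit".
- **Section 1.25** says "At follow up visit, we will collect patient drug logs and any comments or notes regarding possible side effects". It also gives patients contact details for reporting problems promptly.
- **Section 1.3** marks only study drug administration in the Day 1-6 column. The next column is Visit 2, Day 30 +/-7.

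Section 1.22 attaches a consequence to completion: "Patients who do not complete the full course of study drug/placebo will be noted in the results tables". The same sentence goes on to leave these patients out of the statistical analysis of outcomes. Section 1.30 names an intention-to-treat dataset of all randomized participants, 30 per arm. Section 1.26.8 lets participants complete Visits 2 and 3 by certified mail. It lists the SIT and the QOD and does not mention the log or unused product.

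**The concern.** The only physical check on the log depends on the fact it is meant to establish. Product is requested if doses were missed. A participant whose log shows every dose taken has no stated reason to bring anything back, and no count is recorded for anyone. The outpatient supply therefore cannot be reconciled for those reporting full adherence.

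Two things follow. First, 1.22 acts on a completion status that cannot be verified and is not defined: 1.16.2 lets a late dose be skipped, and no section says whether one skipped dose makes the course incomplete. Second, if the trial finds no difference, the reader cannot judge whether NAC failed or was not taken. The population adds some weight to this, since section 1.9 itself lists memory problems among the common sequelae of head injury.

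**Working it through.** **1. Doses and grams (1.16.2).**
Doses: 1 + (2 × 4) + (2 × 2) = 13, of which 12 are at home (12/13 = 92%).
Grams: 4 + (2 × 2 × 4) + (2 × 1.5 × 2) = 4 + 16 + 6 = 26, of which 22 are at home (22/26 = 85%).

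**2. Time to the first scheduled inquiry (1.3).**
Visit 2 window: 30 - 7 = Day 23 to 30 + 7 = Day 37.
Gap from the last planned dose on Day 6: 23 - 6 = 17 days to 37 - 6 = 31 days.

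**3. What the site would hold for each kind of participant (1.17.1, 1.19, 1.26.8).**

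| Participant | Log | Product returned | Can the site tell? |
|---|---|---|---|
| Takes all doses | Complete | None | No count to confirm it |
| Misses doses and logs this | Incomplete | Requested | Yes |
| Misses doses, logs them as taken, returns nothing | Complete | None | No; looks like row 1 |
| Uses the mail option | Not mentioned | Not mentioned | Possibly no record at all |

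**4. The plan's sample size (1.29).** Difference 25 - 17 = 8, SD 10, two-sided alpha 0.05, power 0.8:
n = 2 × 10² × (1.960 + 0.842)² / 8² = 24.5, so 25 per arm. Adding the 5 per arm allowed for losses gives 30. The plan's figure is reproduced.

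**5. Illustration of undetected non-adherence.** Assumptions: a fraction q of the NAC arm takes little of the home course, logs it as complete and gains nothing, including from the observed loading dose. SD stays at 10 and all 30 per arm are analysed. The documents give no value for q, so 10% and 20% are shown.
Diluted difference = 8 × (1 - q). Noncentrality = difference / (10 × √(2/30)) = difference / 2.582. Power is from the two-sided t-test on 58 degrees of freedom.

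| q | Difference | Noncentrality | Power |
|---|---|---|---|
| 0 | 8.0 | 3.10 | 0.861 |
| 10% | 7.2 | 2.79 | 0.783 |
| 20% | 6.4 | 2.48 | 0.684 |

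**6. If the same fractions were detected and excluded from both arms under 1.22.** With 27 or 24 per arm and an 8-point difference, power is 0.822 or 0.774. These figures are higher than in step 5, so power is not the argument against exclusion. The argument is that exclusion selects participants on behaviour after randomization, which the all-randomized set in 1.30 is meant to avoid.

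**The case against.** The plan openly chooses log-based adherence for a six-day course at a single site, and that is a defensible choice. Five points can be made for it.

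- The log is meant to be filled in dose by dose, with notes on side effects. A reader might infer that doses and side effects are simply recalled weeks later. Sections 1.19 and 1.25 describe a running record collected later, and back-filling is only a possibility.
- A reader might infer that there is no contact at all before Visit 2. Section 1.25 lets patients report problems, and 1.26.7 has those not yet seen at follow-up phoned if a serious adverse event occurs. What is absent is scheduled contact, and neither route asks about adherence.
- The return sentence can be read as asking for whatever is left over, since someone who missed nothing should have nothing left. On that reading the gap is narrower: no return of empty containers and no recorded count.
- A participant willing to falsify a log can also discard capsules.
- A call after the last dose cannot rescue a missed one, and a count that fed the exclusion rule in 1.22 would remove more randomized participants.

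All five stand as limits on the point. They do not supply the missing check: under any reading, a complete log with nothing returned is accepted as it is, and the mail route does not mention collecting either item.

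**Conclusion.** The gap is real and cheap to close. With 92% of doses and 85% of the drug taken at home, adherence rests on a log that nothing independent can check, and no adherence inquiry is scheduled until 17-31 days after the last dose.

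Two stronger readings go too far. One is that completion settles who is analysed. Section 1.22 says so, but 1.30 names all randomized participants, so the documents conflict and have to be reconciled. The other is that completion will be misclassified and the trial will lose power. The documents give no non-adherence rate. The fall from 0.86 to 0.78-0.68 depends on the assumed 10-20%, on no benefit from the observed 4 g, and on no attrition from 30 per arm.

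Counting capsules would not restore that power in an all-randomized analysis. What it offers is a way to describe adherence credibly and to interpret a null result. This is a worthwhile improvement to the plan, not a flaw that invalidates it.

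**What to change.** - **1.17.1:** replace the conditional sentence. Every participant returns the container and any remaining capsules, empty or not, together with the log, at Visit 2 or by the mail route. A coordinator blind to allocation records the count.
- **1.26.8:** add the log and container to the items sent back by certified mail.
- **1.19:** describe adherence by arm from the count together with the log, and define completion in advance.
- **1.22 and 1.30:** reconcile them, with all randomized participants as the primary set and completers as a supportive analysis only. Adherence data should not remove anyone from the primary comparison. This should be settled together with the count, so that the count does not lead to more exclusions.
- **1.3:** add one scripted coordinator call shortly after the last home dose. It records doses taken, side effects and concomitant medication while they are recent, and reminds the participant to return the container.

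The cost is a few sentences, one schedule column, about 60 short calls and a capsule count at a visit already planned. A count cannot prove ingestion, and the call cannot recover missed doses.

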1.17.2 FORMULATION, APPEARANCE, PACKAGING, AND LABELING

Research pharmacy will prepare and label study drug or placebo appropriately for double-blind study.

1.17.3 PRODUCT STORAGE AND STABILITY

Patients will receive a 6-day course of medication. This is to be stored at room temperature. Drug will be considered expired after 1 month.

1.17.4 PREPARATION

No preparation will be required. Drug or placebo will be ready-to-use capsule to be taken orally.

1.18 MEASURES TO MINIMIZE BIAS: RANDOMIZATION AND BLINDING

To minimize bias, this will be a randomized double-blind trial. We will use the Jackson Health System Research Pharmacy to prepare study drug or placebo, using their randomization procedures and

labeling. Trial randomization codes will be maintained until planned enrollment is reached and the final patient has completed the 2 planned follow up visits. There are no planned lab studies or measures that would be expected to lead to inadvertent unblinding. If there are serious adverse events (SAEs), this will be reported to the PI and unblinding for the affected subject would be performed.

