1.26.2 DEFINITION OF SERIOUS ADVERSE EVENTS (SAE)

An adverse event (AE) or suspected adverse reaction is considered "serious" if, in the view of either the investigator or sponsor, it results in any of the following outcomes: death, a life-threatening adverse event, inpatient hospitalization or prolongation of existing hospitalization, a persistent or significant incapacity or substantial disruption of the ability to conduct normal life functions, or a congenital anomaly/birth defect. Important medical events that may not result in death, be life-threatening, or require hospitalization may be considered serious when, based upon appropriate medical judgment, they may jeopardize the participant and may require medical or surgical intervention to prevent one of the outcomes listed in this definition. Examples of such medical events include allergic bronchospasm requiring intensive treatment in an emergency room or at home, blood dyscrasias or convulsions that do not result in inpatient hospitalization, or the development of drug dependency or drug abuse.

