1.26.3.2 RELATIONSHIP TO STUDY INTERVENTION

All adverse events (AEs) must have their relationship to study intervention assessed by the clinician who examines and evaluates the participant based on temporal relationship and his/her clinical judgment.

The degree of certainty about causality will be graded using the categories below. In a clinical trial, the study product must always be suspect.

- Related The AE is known to occur with the study intervention, there is a reasonable possibility that the study intervention caused the AE, or there is a temporal relationship between the study intervention and event. Reasonable possibility means that there is evidence to suggest a causal relationship between the study intervention and the AE.
- **Not Related** There is not a reasonable possibility that the administration of the study intervention caused the event, there is no temporal relationship between the study intervention and event onset, or an alternate etiology has been established.

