1.26.3.3 EXPECTEDNESS

PI will be responsible for determining whether an adverse event (AE) is expected or unexpected. An AE will be considered unexpected if the nature, severity, or frequency of the event is not consistent with the risk information previously described for the study intervention.

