1.26.4 TIME PERIOD AND FREQUENCY FOR EVENT ASSESSMENT AND FOLLOW-UP

The occurrence of an adverse event (AE) or serious adverse event (SAE) may come to the attention of study personnel during study visits and interviews of a study participant presenting for medical care, or upon review by a study monitor.

All AEs including local and systemic reactions not meeting the criteria for SAEs will be captured on the appropriate case report form (CRF). Information to be collected includes event description, time of onset, clinician's assessment of severity, relationship to study product (assessed only by those with the training and authority to make a diagnosis), and time of resolution/stabilization of the event. All AEs occurring while on study must be documented appropriately regardless of relationship. All AEs will be followed to adequate resolution.

Any medical condition that is present at the time that the participant is screened will be considered as baseline and not reported as an AE. However, if the study participant's condition deteriorates at any time during the study, it will be recorded as an AE.

Changes in the severity of an AE will be documented to allow an assessment of the duration of the event at each level of severity to be performed. AEs characterized as intermittent require documentation of onset and duration of each episode.

PI will record all reportable events with start dates occurring any time after informed consent is obtained until 7 (for non-serious AEs) or 30 days (for SAEs) after the last day of study participation. At each study visit, the investigator will inquire about the occurrence of AE/SAEs since the last visit. Events will be followed for outcome information until resolution or stabilization.

Adverse Event reporting will adhere to all established guidelines, as described below.

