1.26.6 SERIOUS ADVERSE EVENT REPORTING

The study clinician will immediately report to the UM Human Subjects Research Office any serious adverse event, whether or not considered study intervention related, including those listed in the protocol or investigator brochure and must include an assessment of whether there is a reasonable possibility that the study intervention caused the event. Study endpoints that are serious adverse events (e.g., all-cause mortality) must be reported in accordance with the protocol unless there is evidence suggesting a causal relationship between the study intervention and the event (e.g., death from anaphylaxis). In that case, the investigator must immediately report the event to the sponsor.

All serious adverse events (SAEs) will be followed until satisfactory resolution or until the site investigator deems the event to be chronic or the participant is stable.

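### Section 1.18 unblinds a participant after every SAE, whether or not the allocation is needed; the effect is probably small but is cheap to avoid

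*Combined protocol and SAP*

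**What the plan says.** Section 1.18 of the combined protocol and SAP keeps the randomization codes until enrolment is complete and the last participant has finished both follow-up visits. It then makes one exception: "If there are serious adverse events (SAEs), this will be reported to the PI and unblinding for the affected subject would be performed". No other section narrows that rule.

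The trigger is wide. The SAE definition (1.26.2) includes "inpatient hospitalization or prolongation of existing hospitalization". Section 1.26.6 requires reporting of "any serious adverse event, whether or not considered study intervention related". Section 1.26.4 collects events from consent "until 7 (for non-serious AEs) or 30 days (for SAEs) after the last day of study participation".

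The judgements made on an SAE sit with different people:

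- Relatedness is "assessed by the clinician who examines and evaluates the participant based on temporal relationship and his/her clinical judgment" (1.26.3.2). Severity is also a clinician's assessment (1.26.4).
- On expectedness, "PI will be responsible for determining whether an adverse event (AE) is expected or unexpected" (1.26.3.3).
- On withdrawal, 1.22 states: "An investigator may discontinue or withdraw a participant from the study for the following reasons". One listed reason begins "If any clinical adverse event (AE), laboratory abnormality, or other medical condition or situation occurs" and turns on the participant's best interest.

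Section 1.22 replaces participants who are withdrawn after receiving study drug. It leaves those who did not finish the course out of the outcome analysis. Section 1.30 names an ITT set of all randomized participants.

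**The concern.** In a double-blind trial the code is normally broken for one person when knowing the allocation would affect that person's care. Section 1.18 breaks it whenever an event meets a regulatory definition of seriousness. Many such events in a trauma population, such as a readmission for another injury, need have nothing to do with a one-week oral course.

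Two things are exposed. The first is the set of judgements recorded about the event. If the assessor may already know the arm, severity, relatedness and expectedness are no longer reliably blinded. Severity feeds the planned safety summary (1.31.4), relatedness goes into the SAE report (1.26.6), and expectedness is one of the criteria for an unanticipated problem (1.27.1). The second is the discretionary decision to withdraw someone whose allocation may be known, before the last SIT has been obtained.

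**Working it through.** The plan attaches no figure to this point and gives no expected SAE rate, so there is nothing to reproduce. The check is of how far the rule reaches and what it can affect.

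**1. How much of the SAE window lies outside dosing.** Inputs: a loading dose before discharge plus a 6-day outpatient course (1.16.2, 1.19), about 7 days; last visit at 3 months (synopsis and endpoints), although the schedule in 1.3 labels it Month 4; SAE collection for 30 days after last participation (1.26.4). I take months of 30 days and the last visit as the end of participation.

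- Last visit at 3 months: window = 90 + 30 = 120 days. Outside dosing = 120 - 7 = 113 days, and 113/120 = 94%.
- Last visit at Month 4: window = 120 + 30 = 150 days. Outside dosing = 150 - 7 = 143 days, and 143/150 = 95%.

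These are shares of calendar time, not of events, which may cluster early.

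**2. What unblinding can affect in each part of the window.**

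- *During dosing (about 7 days).* Section 1.21 already stops drug and withdraws the participant for a possible adverse effect, without reference to allocation, and 1.22 then excludes that participant as a non-completer. Unblinding adds discretion only for SAEs that are not seen as possible adverse effects.
- *End of dosing to last SIT (90 - 7 = 83 days, or 120 - 7 = 113 days).* The exclusion in 1.22 does not apply to someone who finished the course. An investigator may still withdraw that person, who is then replaced. Section 1.21 promises continued outcome collection after drug is stopped for an adverse effect; 1.22 makes no such promise for other withdrawals, and no missing-data method is given. A later SIT could be lost.
- *Last SIT to 30 days afterwards.* The SIT can no longer be affected. Only the judgements on the event remain.

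**3. Order of events.** Sections 1.18, 1.26.3.2, 1.26.3.3 and 1.26.4 do not say whether the judgements come before or after the code break. Unblinded assessment is therefore permitted, though not prescribed.

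**4. Whether safety reporting needs the code.** The SAE report in 1.26.6 requires a causality assessment, and 1.27.2 lists the contents of an unanticipated-problem report. Neither asks for the allocation, so the automatic break serves no reporting step in the protocol.

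**The case against.** The strongest reply is that little can go wrong. Only the affected participant is unblinded. The primary outcome is a 40-item forced-choice test that participants complete themselves (1.24), so the score is hard to influence. The earlier study of the same regimen reported no adverse effects (1.9), so there may be no SAEs. The research pharmacy follows its own double-blind procedures (1.17.1), which are not reproduced and may restrict who sees the code. All of this stands, and it limits the size of the point. It does not alter what 1.18 tells staff to do.

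Four stronger readings are tempting, and the documents do not support them.

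- *Withdrawal after unblinding removes the participant from the analysis.* The exclusion in 1.22 is for people who did not complete the course, not for everyone withdrawn. During dosing, 1.21 largely leads to the same exclusion whatever the allocation.
- *The PI learns the allocation and then controls every later judgement.* Section 1.18 names no recipient. Relatedness belongs to the examining clinician and withdrawal to an investigator; only expectedness is given to the PI.
- *Biased relatedness and expectedness calls distort the safety summary.* Section 1.31.4 reports the number of AEs and their severity. Of the three judgements, only severity enters it.
- *The bias in the SIT comparison can be calculated.* That would need an SAE count, removals concentrated in one arm, and removed participants who score low. The documents give none of these. The first full SIT is at day 30, so a removal during dosing cannot be chosen on that score, and replacement would dilute any shift.

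**Conclusion.** The point holds as a procedural weakness. As written, 1.18 breaks the blind after every SAE without a test of need and without a named recipient, across a window that lies about 94 to 95% outside the dosing period. It leaves severity, relatedness and expectedness open to unblinded assessment, and it leaves a discretionary withdrawal possible between the end of dosing and the last SIT.

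The likely effect is small, and with no SAEs it is zero. No numeric bias estimate is justified. The conclusion assumes that 1.18 is followed literally and that no pharmacy procedure outside the protocol narrows it. It does not depend on who receives the code, because nothing in the text restricts that. This is a cheap improvement, not a threat to the trial's main result.

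**What to change.** Replace the last sentence of 1.18 with a rule that covers the following:

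- An SAE is reported to the PI without the allocation.
- The research pharmacy releases the code when the treating clinician requests it for that participant's care, and to that clinician only.
- Severity, relatedness and expectedness are recorded blinded, without delaying a release needed for care.
- Each code break is logged with its date and reason.
- The participant's SIT and QOD continue to be collected.

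Whether an unblinded participant is analysed in the randomised arm cannot be settled in 1.18 alone. Section 1.22 excludes non-completers and 1.30 names all randomized participants; the same edit must reconcile the two.

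The cost is a request step before the allocation is released, a pharmacy log, and the matching edits to 1.22 and 1.30. Sample size, visits and treatment do not change. One limit remains: co-investigators oversee the trauma unit (1.24), so the treating clinician may also be an investigator. Recording the judgements blinded matters most in that case.
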